Study Name: Pilot Study: Prospective comparison of ICG microangiography and conventional angiography in severe frostbite

Principal Investigator: [name]

Date Submitted: December 1, 2022

1. Summary

Severe frostbite injury is a significant cause of morbidity in northern climates. Here in Minnesota, we have some of the highest numbers of severe frostbite injuries in North America¹. As a result, at Regions Hospital we have the best opportunity to study this disease process and improve outcomes for frostbite patients. The diagnostic methods for severe frostbite injury vary from institution to institution and there is no standard practice. Commonly utilized methods include conventional angiography, Technetium 99 triple phase bone scans, SPECT studies, Indocyanine Green microangiography, and doppler studies¹⁻⁴.

Regions Hospital is one of the busiest institutions utilizing conventional angiography. Conventional angiography can fully delineate the vascular occlusion (cut off) found in severe frostbite patients in highly granular detail. However, this method of diagnosis is very labor intensive and not without risk (pseudoaneurysms, contrast induced nephropathy, complications associated with lying flat for up to 72 hours, etc^{2,5-6}). By contrast, Indocyanine Green (ICG) microangiography is a relatively low risk imaging modality that can be done at the bedside. This method shows the microvascular soft tissue perfusion and demonstrates where the tissue is ischemic in severe frostbite injury. ICG imaging involves delivering a small amount of ICG dye (5 mg) via peripheral IV and using a specialized camera that captures the dye fluorescing in infra-red light.⁷ This method of imaging is FDA approved and has been shown to be highly accurate at predicting final amputation level in severe frostbite injury⁸.

The proposed pilot study aims to directly compare conventional angiography imaging to ICG microangiography in adult patients with severe frostbite. Severe frostbite is defined as 4th degree: frostbite resulting in vascular occlusion and tissue ischemia. Both imaging modalities have been used for the diagnosis and monitoring of severe frostbite injury but there has never been a study directly comparing these two imaging modalities^{2,7-8}. We will be obtaining consent from adult patients with severe frostbite injury who are undergoing intra-arterial thrombolysis. During their treatment, an angiography will be performed according to the Regions Hospital standard of care protocol, followed immediately by an ICG microangiography image. These two diagnostic images will be directly compared by a radiologist and a burn surgeon to determine the image concordance or discordance. We will also monitor patients for potential side effects or adverse reactions to the ICG imaging, but as stated above, the ICG microangiography is low-risk and we do not anticipate any adverse reactions related to this procedure.

Pending the results of this study, we will pursue a full-scale version of this study, which will track patients in a longitudinal manner to determine the outcome of their frostbite treatments. The proposed pilot study is designed to assess feasibility, the degree of concordance or discordance between the two imaging modalities, and side effects of imaging.

2. Study Aims

Primary Outcome: Angiography and ICG microangiography imaging concordance/discordance.

Research question: Does the vascular cut off on conventional angiography found in severe frostbite patients correlate with the tissue ischemia demonstrated on ICG microangiography in severe frostbite?

Hypothesis: Conventional angiography can fully delineate the vascular occlusion (cut off) found in severe frostbite patients in highly granular detail. ICG microangiography shows the microvascular soft tissue perfusion and demonstrates where the tissue is ischemic in severe frostbite injury. We hypothesize that these two imaging modalities will be concordant at demonstrating the ischemic tissue present in severe frostbite.

Secondary Outcome: Safety.

Research question: Is indocyanine green safe when delivered in close association with contrast dye (used in conventional angiography)?

Hypothesis: Contrast dye used in conventional angiography is associated with nephrotoxicity and other risks. Indocyanine green dye is generally considered to be a highly safe product with minimal risks associated with administration. It has been used for decades with minimal side effects. It is hypothesized that ICG dye will not result in any increase in risk to the patient when delivered in temporal proximity to conventional dye.

3. Background, Rationale, Significance

Frostbite injury has been a significant cause of morbidity and mortality for as long as humans have experienced cold winters. When frostbite occurs, there are two primary mechanisms through which tissue damage occurs, though the main mechanism we will focus on here is systemic cooling. Frostbite is a multiphase process that starts with systemic cooling. As the body cools, blood is shunted from the extremities to the core to maintain heat in the vital organs. During this shunting, there is extensive vasospasm in the extremities and the tissue becomes ischemic. Upon further cooling, tissue ice crystals form within the cells and interstitial spaces causing desiccation and cell destruction. This occurs in the soft tissues and also affects the endothelium of the micro- and macrovasculature. Clots form in the microvasculature, worsening the ischemia. All ischemic tissues release pro-inflammatory factors, which increase inflammation and worsen clotting.⁹⁻¹⁴

Upon rewarming of the frozen tissues, the reperfusion can worsen the inflammatory state as these factors released by the ischemic tissue are now able to circulate. Rapid rewarming is used as a tool to mitigate this reperfusion injury, but it does not eliminate the damage^{1,15}. After rapid rewarming, the tissue is assessed for the extent of damage to determine next treatment steps. Diagnosis varies by institution, but the main goal of all diagnostic modalities is to determine if there is a vascular cutoff causing tissue ischemia.

At Regions Hospital, the main diagnostic method that has been used for over 20 years is conventional angiography. This clearly demonstrates the microvasculature of the tissues and allows the intra-arterial catheter directed sheaths to be placed to start thrombolytics, heparin, and vasodilators to treat the tissue ischemia². Other diagnostic modalities used elsewhere include Technetium 99 triple phase bone

scans, SPECT imaging, and indocyanine green (ICG) microangiography¹⁶. All of these imaging modalities demonstrate the perfusion of the affected tissue but do not allow for directed delivery of thrombolytics. In institutions that use these imaging techniques, thrombolytics are typically delivered in an intravenous fashion rather than intra-arterial.

ICG microangiography is a technology that has had rapidly expanding applications in recent decades. These have included retinal imaging, determining perfusion of colorectal anastomoses, biliary imaging, and assessing the blood supply of tissue flaps¹⁷⁻¹⁹. It has recently been used in diagnosis of frostbite with good correlation with severe final amputation levels. It is easy to use, non-radiating, can be performed at the bedside, and cheaper than other imaging modalities⁷⁻⁸.

Given that every hospital has different diagnostic and treatment algorithms, these different imaging modalities have rarely been compared in the same patient. The current best metric is comparing the imaging modality with the amount of tissue that is amputated as demonstrated in prior studies cited here. This research application provides a unique opportunity to compare two imaging modalities head-to-head in the same patient and determine their concordance or discordance.

4. Study Design

This pilot study is an unblinded prospective interventional imaging study designed to determine whether ICG microangiography is as accurate as conventional angiography in determining the ischemic tissue present in severe frostbite.

We will capture images of 10 patients who are undergoing conventional angiography and thrombolysis for severe frostbite. All patients will be adults (>18 years old) and able to provide consent for participation in the study. Once the patient has been started on thrombolysis, they will be evaluated for whether they meet the study's inclusion/exclusion criteria, and then approached by a CCRC Clinical Research Coordinator about possible involvement in this research project. If they consent to the study, then the ICG microangiography imaging will be performed immediately following their next conventional angiography session. When a patient is undergoing catheter directed thrombolysis, they have conventional angiography sessions to assess progression every 24 hours for up to 72 hours. In this pilot study, we would administer the ICG microangiography following one of these sessions, after consent is obtained. This imaging would be performed in the IR suite immediately following the conventional angiography session.

This study is quasi-experimental. The inclusion of a second (ICG) imaging technique is not a therapeutic modality and has limited risks to the study participants. ICG dye is very well tolerated and only contraindicated in iodine allergy. There is no radiation associated with this imaging study. Participants will serve as their own controls as they will be receiving both types of imaging.

Population

Patients will be identified by the burn surgeons and advance practice practitioners. They will evaluate the patients to determine whether they meet the inclusion/exclusion criteria of the study.

a. Inclusion criteria

1. Adult (>18 years old) patients
2. Diagnosed with severe frostbite by conventional angiography
3. Undergoing thrombolysis with catheter directed lytics
4. Clinically sober at the time of consent
5. Cognitively able to provide consent as determined by clinician's best judgement
6. Normal kidney function (GFR >60)

b. Exclusion criteria

1. Pregnant. Pregnancy will be determined by standard of care pregnancy test performed on all female frostbite patients who are receiving lytics.
2. Iodine allergy.

c. Sample size

1. Ten ICG images will be performed on 10 unique patients who are already receiving conventional angiography as standard of care.
2. Feasibility: Based on historical data from Regions Hospital between 2006-present, there are typically 20-70 patients per winter who undergo conventional angiography and catheter directed lytics who would be candidates to participate in this study. We anticipate approaching 20 patients to reach our target sample size of 10.

Data collection process

1. Process for identification of patients: All patients undergoing catheter directed thrombolysis for severe frostbite injury are managed primarily by the Burn Team. As such, the burn surgeons and burn advance practice practitioners will be able to identify patients who meet the inclusion criteria for this study.
2. Recruitment: The burn surgeon will identify patients and confirm that they meet the inclusion/exclusion criteria for the study. They will inform the Clinical Research Coordinator from the Critical Care Research Center (CCRC), who will approach the patient about the study and obtain informed consent.
3. Consent: Written consent will be obtained by the CCRC Clinical Research Coordinator who is the Lead Coordinator for this study (see attached ICF). Competency to provide consent will be confirmed by the coordinator obtaining consent by testing for comprehension after the consent conversation and before a signature is obtained.

Data sources

Data sources will include chart review, conventional angiography images, and ICG microangiography images. Images and data will be stored on an encrypted HealthPartners computer at Regions Hospital.

Data acquisition

- Data will be collected by [name], burn surgeon.
- Patient contact by study personnel will include consenting the patient for this study (CCRC Clinical Research Coordinator) and performance of the ICG microangiography study (performed by [name]).
- Data points from the Electronic Medical Records will include:
 - MRNs
 - Last name, first name
 - Basic demographics: age, gender, race, ethnicity
 - Social: substance abuse, mental health diagnoses, housing status
 - Medical: comorbid conditions CAD/vascular disease, diabetes mellitus, renal insufficiency, smoking
- Data from the conventional angiography include:
 - Medications currently being infused
 - Hours of treatment
 - Areas of poor perfusion as measured by the Hennepin Frostbite Score ²⁰ (see attached score sheet)
- Data from the ICG microangiography include:
 - Areas of poor perfusion as measured by the Hennepin Frostbite Score

DATA DICTIONARY GOES HERE

Statistical Analysis Plan

The primary dependent variable in this study is the Hennepin Frostbite Score that will be generated from each imaging technique. We will compute a correlation between the Hennepin Frostbite Score produced by the conventional angiography and the Hennepin Frostbite Score produced by the ICG microangiography. While we predict a high correlation between the scores generated by the two methods, a high correlation does not necessarily imply that there is good agreement between the two methods. Thus, we will also use a Bland-Altman (difference) plot to analyze the agreement between the two imaging techniques.

Power analysis or statement of precision

This will be a small pilot study that will not be adequately powered to determine significance.

5. Interventions and treatments

As previously stated, the main intervention in this study is the performance of an ICG microangiography study immediately following a conventional angiography image in patients who are undergoing catheter directed thrombolysis for severe frostbite injury. This will be a one-time diagnostic measure with no additional follow up or imaging required. This is not a therapeutic intervention, but a secondary imaging study with minimal risk.

6. Setting/Environment/Organizational feasibility

Study participants will be patients who are being treated primarily on the Burn Unit at Regions Hospital. Consent will be obtained while they are inpatient by a CCRC Clinical Research Coordinator. The ICG microangiography imaging will be performed in the Interventional Radiology (IR) suite immediately following the patient's conventional angiography imaging. This has been discussed with the IR leadership and they agree to performing this study in their space (see attached Letter of Support). [name], burn surgeon, will be performing the ICG microangiography and staying in constant communication with the IR staff performing the conventional angiography imaging. Given the small number of images need for this pilot study, this method of communication and number of ICG providers will be adequate.

7. Risks and Benefits

ICG microangiography dye is very safe and well tolerated. It will be delivered via a peripheral IV, which the patient will already have in place per protocol for all patients with severe frostbite injury. The small 5mg dose used for this study has limited possible side effects. There is no radiation exposure for this imaging modality. The only known risk is allergic reaction to the ICG dye. Patients with a known iodine allergy will be excluded from this study due to possible reaction to the conventional angiography. All patients who participate in the study will be monitored following dye administration as standard of care for ICU level patients who have catheter directed lytics being delivered.

Psychological, social, legal, and economic risks are not foreseeable for this study. There is no direct benefit to the patient from participating in this study.

8. Strengths and Limitations

Strengths of the study: this is the first study looking at ICG microangiography and conventional angiography in the same patients. Both techniques have been studied individually but this has never been examined in a head-to-head manner in frostbite. Pending the results of this study, this may help to determine what the true 'gold standard' should be for frostbite imaging.

Limitations of the study: This will be a small pilot study that will not be adequately powered to determine significance. This is also a single institution study and is a single snapshot in time (not longitudinal). Concordance of imaging with long term outcomes will not be calculated as part of this preliminary study.

9. Data Confidentiality and Privacy

All data will be stored on the private HealthPartners computer of [name]. This computer and its contents are stored in a locked office in the Burn Unit and are not accessible to any other members of the research or healthcare teams. Any data that are extracted for analysis and/or publication will be de-identified. After completion of this pilot and any follow up studies, identifiable data will be destroyed by the PI. There is no plan to share these data with other entities.

10. Timeline

The goal timeline for this limited project is to begin winter 2022 (January 2022 – March 2023) to make sure we have enough patients to allow us to collect all 10 images for this study. Data analysis will be completed over the spring and summer to allow for the creation any necessary follow up project for the following winter.

11. Dissemination of data

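### Nothing in the plan requires either Hennepin score to be assigned without knowledge of the other modality, so the primary agreement estimate is open to bias toward concordance

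*Combined protocol and SAP*

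**What the plan says.** Section 2 makes concordance or discordance of the two modalities the primary outcome and states the expected direction: "We hypothesize that these two imaging modalities will be concordant at demonstrating the ischemic tissue present in severe frostbite". The Statistical Analysis Plan takes the Hennepin score from each technique as the primary variable. It correlates the two scores, predicts a high correlation, and adds a Bland-Altman plot because correlation alone does not show agreement.

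On how the images are read, the text offers the following:

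- Section 1: "These two diagnostic images will be directly compared by a radiologist and a burn surgeon to determine the image concordance or discordance". This is the only reading step described.
- Section 4: "This pilot study is an unblinded prospective interventional imaging study". No exception is made for scoring.
- Data acquisition: a Hennepin score is listed under each modality, and "Data will be collected by [name], burn surgeon". The scorer, the reading order and any locking of scores are not stated.
- Section 6: a burn surgeon performs the ICG study in the IR suite straight after the angiogram.
- Inclusion criteria: "Diagnosed with severe frostbite by conventional angiography". Data collection process: "All patients undergoing catheter directed thrombolysis for severe frostbite injury are managed primarily by the Burn Team". The burn team may therefore already know a diagnostic angiogram.

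The attached score sheet is not in the text, and a placeholder stands where the data dictionary belongs.

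**The concern.** An agreement statistic means what it appears to mean only if the two measurements are made independently. A reader who knows the angiographic level of cut-off when marking the ICG image, or the reverse, may be drawn toward it. The correlation then rises, the Bland-Altman limits narrow and the mean difference shrinks. The Bland-Altman plot, added as a safeguard against over-reading the correlation, is exposed to the same influence.

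No hypothesis test or go/no-go threshold is at risk, because the plan has none. What is at stake is the estimate itself. Section 1 names the degree of concordance as something the pilot is to assess and makes a full-scale study depend on the results. Section 8 suggests the findings may bear on which modality should be the reference standard. The limitations listed there do not mention reader bias.

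**Working it through.** **Step 1: is there a masking rule?** Sections 1, 2, 4, 6, 8 and 9, the data collection and data acquisition text, and the SAP were checked for any statement on who scores, how many readers there are, in what order they read, or whether a score is fixed before the other image is seen. There is none. The absence is of visible text only, since the score sheet and data dictionary cannot be checked.

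**Step 2: what figure does the plan give?** None to reproduce. It states 10 patients with one image pair each, without an assumed correlation, standard deviation, acceptable limits or power. The size of any bias therefore cannot be derived, and what follows is an illustration.

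**Step 3: direction and size under an assumed pull.** Let x be the first score and y0 the second score as it would be if masked, with equal variances and true correlation ρ. Suppose the unmasked second score is y = (1 − w)·y0 + w·x, where w is the fraction by which it is pulled toward x.

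- Differences: y − x = (1 − w)(y0 − x). The mean difference and the SD of the differences both shrink by the fraction w, whatever ρ is.
- Correlation: r = [(1 − w)ρ + w] / √[(1 − w)² + w² + 2w(1 − w)ρ].

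With ρ = 0.70 and w = 0.25 (both assumed): numerator 0.75 × 0.70 + 0.25 = 0.775; denominator √(0.5625 + 0.0625 + 0.2625) = √0.8875 = 0.942; r = 0.82. The limits narrow by 25%. If the mean difference is 0, each limit moves inward by 0.25 × 1.96 = 0.49 SD of the differences.

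Across a range of assumptions:

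| True ρ | w = 0.10 | w = 0.25 | w = 0.50 |
|---|---|---|---|
| 0.60 | 0.66 | 0.76 | 0.89 |
| 0.70 | 0.75 | 0.82 | 0.92 |
| 0.80 | 0.83 | 0.88 | 0.95 |
| 0.90 | 0.92 | 0.94 | 0.97 |

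The effect on r is small when the true correlation is very high. The proportional narrowing of the limits is not.

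**Step 4: set against sampling error at n = 10.**

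- Fisher z interval for an observed r of 0.70: atanh(0.70) ± 1.96/√7 = 0.867 ± 0.741, which gives about 0.13 to 0.92. A shift to 0.82 lies well inside it.
- Standard error of one Bland-Altman limit: √(1/10 + 1.96²/18) = √0.313 = 0.56 SD of the differences. The 0.49 SD move is smaller than one standard error.

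**Step 5: why that does not dispose of it.** Sampling error falls as n grows; w does not. In this model an observed r of 0.82 fits both a true 0.82 with independent reads and a true 0.70 with a 25% pull, and the scores alone cannot tell the two apart.

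**The case against.** The case on the other side has real content.

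- **Section 1 speaks of images, not scores.** The direct comparison may be a separate descriptive step, with each Hennepin score generated independently. That is possible, and a reader who infers that the scores are assigned jointly goes too far. The text leaves it open, and nothing in it secures independence.
- **Unblinded may describe only the procedure.** This is also fair. The word need not refer to scoring, but no masked scoring is added anywhere.
- **The contact with the angiography staff in section 6 is logistical.** This stands. The surrounding text concerns coordinating a small number of studies and does not say that findings or scores are passed on. It should not be used as evidence of unmasking.
- **The ICG operator may not be a scorer.** The documents do not say that the burn surgeon of section 1 is the one who performs ICG, or that the burn surgeon who collects the data assigns the scores.
- **The model allows only pull toward agreement.** This is correct. Readers asked to look for discordance could exaggerate differences instead. Pull toward agreement is the more worrying direction because it coincides with the hypothesis, but it is an assumption.
- **It is a 10-patient pilot with power disclaimed, and sampling error is at least as large as the illustrated bias.** This is true and limits the weight of the point. It does not answer it, because masking addresses an error that sample size does not.

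**Conclusion.** The gap holds as a risk, not as demonstrated bias. The primary outcome is agreement between two scores, and the plan as written permits either score to be assigned with the other image or score in view. The likely direction is toward the stated hypothesis. The size is unknown. The illustration of 0.70 becoming 0.82, with limits 25% narrower, rests wholly on assumed values of ρ and w and is within sampling error at n = 10.

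A reader might infer that the pilot's concordance result is bound to be inflated, or that both scores come from one unmasked reading. The documents support neither. If the score sheet or data dictionary already holds a masked-reading rule, the remaining defect is that the SAP does not state it. This is an inexpensive improvement worth making before images are scored.

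**What to change.** In the data acquisition and SAP sections:

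1. Name the scorer of each modality, from the radiologist and burn surgeon already in section 1.
2. Require each Hennepin score to be assigned from coded stored images, then recorded and locked without access to the paired image or its score. The plan already keeps the images: "Images and data will be stored on an encrypted HealthPartners computer at Regions Hospital".
3. Do the study scoring after the patient's treatment imaging is complete, so that no angiogram is withheld from care. Section 4 says of these patients that "they have conventional angiography sessions to assess progression every 24 hours for up to 72 hours".
4. Base the correlation and the Bland-Altman plot on the locked scores, and make the side-by-side comparison a descriptive step after locking.
5. If one person scores both modalities, use separate sittings in random order. If different people do, report that reader and modality are confounded.

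Adjust section 9, which keeps the study computer closed to the rest of the team, so that the scorers and whoever codes the images can reach them. Report as a limitation that masking is incomplete: the ICG operator, the burn team or the radiologist may know the clinical angiogram.

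**Cost.** A short paragraph, an access change, and some coding and reading time. With one scorer per modality there are 10 × 2 = 20 scores, which the analysis needs anyway. No extra reader, procedure or patient contact is required. The downsides are delayed scoring and masking that stays imperfect.

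### The secondary safety hypothesis claims no increase in risk, but the plan has no safety comparison that could support it, and the visible text gives no observation window or safety summary

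*Combined protocol and SAP*

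**What the plan says.** All references are to the combined protocol and SAP.

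- **Purpose.** Section 1 says "We will also monitor patients for potential side effects or adverse reactions to the ICG imaging". Besides feasibility, it lists among the things the pilot will assess "the degree of concordance or discordance between the two imaging modalities, and side effects of imaging".
- **Outcome and hypothesis.** Section 2 makes safety the secondary outcome. It asks "Is indocyanine green safe when delivered in close association with contrast dye" and answers with the hypothesis that "ICG dye will not result in any increase in risk to the patient when delivered in temporal proximity to conventional dye".
- **Timing.** Section 4 says that after consent, "then the ICG microangiography imaging will be performed immediately following their next conventional angiography session". During catheter-directed treatment, "they have conventional angiography sessions to assess progression every 24 hours for up to 72 hours". One inclusion criterion is "Diagnosed with severe frostbite by conventional angiography", so every participant has had at least one contrast study before the one paired with ICG.
- **Controls.** Section 4 calls participants their own controls and gives as the reason that each has both types of imaging.
- **Data.** Under Data sources: "Data sources will include chart review", plus the two sets of images. The data-point lists are introduced as inclusive, and the data dictionary appears only as a placeholder.
- **Analysis.** The Statistical Analysis Plan names a correlation and a Bland-Altman plot, both on the Hennepin score. The power statement says that the pilot is too small to establish significance.
- **Monitoring.** Section 7 names allergic reaction as the one known risk of ICG and describes ICU-level standard-of-care monitoring after the dye.

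**The concern.** A hypothesis of no added risk needs a reference: the risk with contrast alone. The plan supplies none, and its analysis section does not mention safety. If the study is run exactly as written, the investigators may see no reactions in 10 patients and report that the hypothesis was confirmed. The data could not carry that conclusion, however cleanly they were collected.

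The undefined window adds a smaller problem. Further contrast sessions can follow the ICG session, so whether a later event counts as following ICG would be decided after the fact. Section 1 makes a full-scale study depend on the pilot's results, so an unsupported safety statement could be carried forward into that study.

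**Working it through.** **1. What the hypothesis requires.** Write p₁ for the risk of an adverse event after contrast followed by ICG, and p₀ for the risk after contrast alone. The hypothesis is p₁ − p₀ ≤ 0. To support it, the study must estimate both terms or take p₀ from a stated source.

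**2. Where p₀ could come from.**

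| Possible reference | In the plan? |
|---|---|
| Separate contrast-only group | No; all 10 participants receive ICG |
| Historical or published event rate | None given for this purpose |
| Own-control statement (section 4) | Justified by imaging; at the paired session each patient gets both dyes, one straight after the other |
| Earlier contrast-only sessions in the same patients | They exist, through the diagnostic angiogram, but no safety use of them is planned |

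The last row is the only within-patient candidate, and it would be a weak one. The ICG session always comes after the contrast-only session. Any difference would therefore mix ICG with cumulative contrast, session order and time on treatment. The design gives data on p₁ only.

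**3. What would be reported.** The two named analyses both use the Hennepin score. Neither produces an event count or rate.

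**4. Window.** Section 7 says where monitoring takes place but not when it ends. Section 5 says that no additional follow-up is required, which does not define a window either. With sessions every 24 hours for up to 72 hours, contrast may be given again after ICG.

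**5. What 10 patients can say about p₁.** The documents give no event rate, margin or significance level, so there is no safety figure of theirs to reproduce. The number 10 comes with a recruitment expectation (20 approached to reach 10), not a statistical derivation. The only input is n = 10, from the Sample size subsection. The exact upper limit after 0 events solves (1 − p)¹⁰ = α:

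- One-sided 95%: p = 1 − 0.05^(1/10) = 0.2589, or 25.9%.
- Two-sided 95%: p = 1 − 0.025^(1/10) = 0.3085, or 30.8%.

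For 1 event in 10, the Clopper-Pearson 95% interval is 0.3% to 44.5%.

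The chance of seeing at least one event is 1 − (1 − p)¹⁰. For assumed true rates (none is given in the documents) it is:

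| Assumed true rate | Chance of at least one event in 10 |
|---|---|
| 1% | 9.6% |
| 2% | 18.3% |
| 5% | 40.1% |
| 10% | 65.1% |

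At a true rate of 5%, a clean record would still occur about 60% of the time (100% − 40.1% = 59.9%). These figures show how a descriptive result should be worded. They follow from the disclosed sample size and do not measure the gap, which is the absent comparison.

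**The case against.** The strongest defence has four parts.

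- **The hypothesis is an expectation, not a test.** No test is specified, section 1 says that no reactions are anticipated, and the pilot's stated purpose regarding side effects is already descriptive. This is fair, and it is why rewording is enough. But section 2 still sets the sentence as the formal hypothesis of the secondary outcome, and results will be read against it.
- **Low power is disclosed.** This stands as an answer to any complaint about the sample size. A reader might infer that 10 patients is itself an error; the documents do not support that, because they openly describe a small pilot. The disclosure concerns significance, however. It does not supply a comparator, a window or a summary, and a larger study of the same design would have the same gap.
- **Safety data may well be collected.** A reader might infer from the visible lists that no adverse-event information will be recorded. The documents do not support that. Monitoring is stated in sections 1 and 7, chart review is a source, the lists are open-ended, and the data dictionary cannot be seen. A missing field is therefore only a possibility.
- **The named ICG risk is narrow.** Allergic reaction limits what would plausibly be attributed to ICG, and this softens the window problem. It does not remove it, because no duration or attribution rule is given. The hypothesis is also introduced with contrast nephrotoxicity and other risks, not with allergy alone.

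**Conclusion.** The point holds in a limited form and should be fixed. The secondary hypothesis is comparative, and the plan contains no safety comparison, so a conclusion of no increase in risk could not be supported whatever the 10 patients show. The absence of a comparison and of a safety summary in the analysis section can be read directly from the text. The absence of a window holds for the visible text. Nothing is concluded about whether an adverse-event field exists.

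At best, the study can describe p₁. With no events, it would exclude only rates above about 26% (one-sided 95%) or 31% (two-sided 95%). This rests on n = 10, one ICG study per patient, and complete ascertainment. The concordance analysis is not affected, and no stated decision rule depends on the safety result, which limits the consequence.

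**What to change.** 1. **Section 2.** Replace the hypothesis with a descriptive aim, for example: to describe adverse events recorded after ICG given immediately after contrast.
2. **Statistical Analysis Plan.** Add the number and proportion of patients with any event after ICG, with exact Clopper-Pearson 95% confidence intervals. State in advance that 0/10 would exclude only true rates above about 26% (one-sided 95%) or 31% (two-sided 95%), and that events cannot be attributed to ICG rather than to the contrast given just before it.
3. **Data collection.** To support this, record from the chart each event and its onset time relative to the ICG injection, over a window that the investigators set within the admission. List events after a later contrast session separately. If the data dictionary already holds such fields, refer to them.

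**Cost.** One reworded sentence, one SAP paragraph and a little chart review for 10 inpatients, with no added test, visit or follow-up. The downside is a less favourable safety claim.
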